#### 9.7. Overdose

As per the SmPC for dexamethasone, reports of acute toxicity and/or deaths following overdose with glucocorticoids are rare.

Overdoses are not anticipated as participants will be given only two pre-measured doses of the IMP (or matched placebo). As per the risk section 2.4, the dexamethasone SmPC recommends dosages which are much higher than the total dosage of 16mg of dexamethasone (2 x 8mg doses) that will be dispensed to intervention participants in this trial.

# 9.8. Reporting urgent safety measures

The Sponsor, CI, co-lead, PI, DMC and/or TSC may take appropriate urgent safety measures (USM) in order to protect the participants of a clinical trial against any immediate hazard to their health or safety.

If a PI implements a USM at site they must inform the CI immediately (see contact details in key trial contacts section and copy ExeCTU; [contact]). If time permits it, the investigator

should discuss any proposed actions with the CI prior to implementation. A record of all discussions, decisions, actions etc must be recorded in the Investigator Site File.

The CI will inform the Sponsor within 24 hours to discuss the hazard and any actions taken (prior to implementation if time allows). USMs identified shall take immediate effect and the CI or Sponsor will telephone the REC and MHRA ideally within 24 hours (no later than 3 days) to discuss the event with a medical assessor. The CI, Sponsor (or delegate) will further notify the REC and MHRA in writing within 3 days from the date the measures were taken.

If the CI and the Sponsor consider the USM to affect all participants, ExeCTU will inform all PIs of the USM under the CIs oversight.

# 9.9. The type and duration of the follow-up of participants after adverse reactions

If a participant has an adverse reaction (AR) whilst in hospital they will be monitored until a resolution or stabilisation is reached.

# 9.10. Development safety update reports

A DSUR will be provided to the MHRA and REC by ExeCTU at the end of each reporting year. The CI (or designated representative) in collaboration with ExeCTU will prepare all relevant information for the DSUR. The sponsor will review the DSUR prior to submission and the CI will review the clinical sections and provide final sign off prior to submission.

# **10. STATISTICS AND DATA ANALYSIS**

# 10.1. Sample size calculation

Participants will be randomised on a 1:1 basis to receive dexamethasone plus usual care or placebo plus usual care. The required sample size has been calculated based on detecting a between-group difference in total pain, from baseline over the first 3 days post-randomisation, of 10 points, based on a standardised area-under-the-curve approach (on a scale of 0-100), with pain NRS collected twice-daily.

The minimum clinically important difference (MCID) in pain is 10 points, based on previously reported emergency care literature. The conservative SD estimate (30 points) is based on previous cellulitis trials reporting pain at single time points, reviewed in a recent meta-analysis. Based on these assumptions, the target standardised effect size is 0.33. This estimate of the pooled SD will be reviewed, blinded, at the end of the internal pilot phase.

191 participants in each allocated group with primary outcome data will give 90% power to detect the MCID of 10 points, assuming a standard deviation (SD) of 30 points, at the two-sided 5% statistical significance level. The recruitment target is 450 participants (225 per allocated group), allowing for up to 15% of participants not returning any pain score 24 hours after the baseline score.

#### Planned recruitment rate

It is estimated (using NHS Digital hospital episode statistics data and multi-site audits) that in summer months, on average 50 people will present to each site each month and  $\sim$ 50% will be eligible to take part. It is estimated  $\sim$ 50% of eligible patients will be approached, of whom  $\sim$ 35% will be randomised,

giving mean recruitment rate/site/month of ~4 participants once recruitment processes are fully established. However, as incidence rates of cellulitis vary by season (higher rates in the summer months) lower recruitment rates of ~2/site/month are anticipated during the non-summer months. Our projected recruitment period therefore allows for both seasonality and staggered site opening.

#### 10.2. Statistical analysis plan

A detailed statistical analysis plan (SAP) will be written, following published guidelines, approved by the TSC and made publicly available before the follow-up period concludes. Any amendments will be discussed with the TMG and TSC, and documented with date and details of the amendment.

Results will be reported following the CONSORT statement and relevant extensions (Patient Reported Outcomes; Pragmatic Trials).

Throughout the analysis, emphasis will be placed on estimation rather than hypothesis testing. Where hypothesis tests are carried out, these will be at the 5% two-sided level for primary and secondary outcomes.

#### 10.2.0. Summary of baseline data and flow of patients

Participants' baseline characteristics will be summarised descriptively overall and by allocated treatment group. There will be no formal between-group testing of baseline data.

Means with standard deviations and ranges will be reported for the continuous variables: baseline pain (NRS, 0-10), age, BMI, NEWS2 Score, clinical frailty scale, index of multiple deprivation, time since cellulitis onset, unless the distributions appear to be skewed in which case medians and interquartile ranges will be reported instead. Percentages and numbers will be reported by category for the categorical variables sex (male/female), ethnicity, self-reported gender, severity of cellulitis (using Eron classification), location of cellulitis (leg/other location), antimicrobial therapy for this episode of cellulitis prior to attending urgent and emergency care (yes/ no), diabetes status (yes/no), current use of intravenous "street" drugs (yes/no), current and recent analgesia including NSAID (yes/no), clinical comorbidities (including peripheral vascular disease, chronic venous insufficiency and morbid obesity), risk factors for steroid adverse events and other clinical details of cellulitis.

Loss to follow-up after randomisation will be reported separately for each group with regards to these variables.

A CONSORT flow diagram will be produced to illustrate the flow of participants through the trial. Specifically, the number of participants approached, eligible, consented and recruited, and assessed at baseline, 3, 14 and 90 days will be illustrated, along with the number of participants withdrawn or loss to follow-up between each data collection time point. The reasons for ineligibility and withdrawal will also be presented.

# 10.2.1. Primary outcome analysis

# General principles for primary analysis of primary outcome

An area under the curve (AUC) approach will be used to capture the primary outcome, total pain experienced over the first 3 days, including baseline. The AUC will be calculated using the trapezoidal rule, by rescaling the numerical rating pain scores (0-10) at each time point to a 0-100 scale, to give a standardised AUC on a scale of 0-100. Participants will be included in the primary intention-to-treat analysis if they contribute at least 2 out of a possible 7 pain scores, with the second pain score being

at least 24 hours after the baseline pain score. Missing pain scores will be imputed using linear interpolation, if scores are available either side of the missing pain score. If final scores are missing, then scores will be imputed using last observation carried forward, a conservative approach.

The primary outcome (pain AUC) will be analysed using a mixed effects linear regression (intention-totreat) model, adjusting for age, sex, baseline pain, severity of cellulitis, antimicrobial therapy for this episode of cellulitis prior to attending urgent and emergency care, diabetes status and severity of cellulitis (Eron Stage1 vs all other stages) as fixed effects and recruitment site as a random effect to account for potential between-site heterogeneity. From the model, the adjusted difference in means for the pain AUC between the dexamethasone and placebo group will be reported with 95% confidence interval. The unadjusted between-group difference in means with 95% confidence interval will also be reported.

#### Estimands framework for primary outcome

The primary estimand of interest is the effect of the addition of dexamethasone to usual care compared to placebo and usual care, which will be addressed by the proposed intention to treat analysis, with a treatment policy strategy applied to intercurrent events, which is a conservative approach. The key intercurrent event of seeking additional healthcare input has been identified.

Any secondary estimands will be defined clearly and a priori in the SAP.

#### Approach to handling missing data for primary outcome

Missing pain scores will be imputed using linear interpolation, if scores are available either side of the missing pain score. If final scores are missing, then scores will be imputed using last observation carried forward, a conservative approach. Different approaches for dealing with missing scores may be considered in a sensitivity analysis, which will be detailed in the SAP.

#### Sensitivity analysis for primary outcome

Sensitivity analysis will be undertaken to check the robustness of the primary analyses to assumptions, in particular with regards to the imputation methods used for missing pain scores in the first 3 days. Multiple imputation using chained equations may be considered. Imputation algorithms will include allocated treatment group, baseline score, centre, minimisation variables and age, sex and baseline characteristics that are predictive of missingness.

If imbalances are noted between the trial groups in other baseline characteristics and thought to be predictive of outcome, then as part of a sensitivity analysis, the analysis will be repeated adjusting for these characteristics in addition to those already listed.

# 10.2.2. Secondary outcome analysis

# General principles for secondary outcomes

If the necessary data assumptions are met, a mixed effects linear regression model will be fitted for the secondary outcomes of PGI-I and pain at 14 days. A mixed effects repeated measures model will be fitted for PGI-I recorded at days 1,2, and 3. In the case of model assumptions not being met, alternative modelling approaches will be considered, depending upon the distribution of the outcomes, such as a mixed effects ordinal logistic models or dichotomising the categories for a logistic regression. Alternative modelling approaches to be considered will be detailed further in the SAP. Mixed effects logistic models (if the number of observed events allow) will be fitted for the dichotomous secondary outcomes; additional antibiotic use post-randomisation to Day 14, (re)admission to hospital by Day 14, any unscheduled health care use until Day 14 and recurrence of cellulitis by Day 90. All models will adjust for the same factors as with the primary analysis of the primary outcome.

For the continuous secondary outcomes with mixed effects linear models fitted, adjusted differences in means between the dexamethasone and placebo group will be reported with 95% confidence intervals. For outcomes analysed using mixed effects logistic regression models, adjusted odds ratios will be reported with 95% confidence intervals. The unadjusted difference in means and odds ratios with 95% confidence interval will also be reported to aid future meta-analysis.

A descriptive analysis will report, by allocated group, on compliance, the amount and type of analgesia taken over the first 3 days, and on the route, type and length of post-randomisation antibiotics prescribed and hospital (re)admission related to dexamethasone use and complications related to dexamethasone use (all until Day 14).

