#### 3.2. Secondary objectives

To determine whether the addition of dexamethasone to treat patients with cellulitis when compared to a control (placebo):

- a) Improves quality of life and other patient reported outcomes,
- b) Reduces subsequent antimicrobial prescribing, analgesia usage and healthcare utilisation
- c) Is cost-effective.

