#### 3.3.1. Secondary endpoints/outcomes

- 1. Health-related quality of life, measured by EQ-5D-5L at Day 3, Day 14 and Day 90 post-randomisation
- 2. Patient Global Impression of Improvement (PGI-I) measured daily for first 3 days and at Day 14 post-randomisation
- 3. Analgesia usage (number and type of analgesia taken over first 3 days) post-randomisation
- 4. Antibiotic usage (route, type, and post-randomisation length of course) up to Day 14 post-randomisation
- 5. (Re)admissions to hospital by Day 14 post-randomisation
- 6. Complications of dexamethasone use by Day 14 post-randomisation
- 7. Unscheduled healthcare usage until Day 14 post-randomisation
- 8. Health, social care and broader societal resource use, measured by a resource use questionnaire based on the Modular Resource Use core module (ModRUM) tailored to the study population, to Day 90 post-randomisation
- 9. Recurrence of cellulitis by Day 90 post-randomisation
- 10. Serious and/or potentially related adverse events by Day 90 post-randomisation
- 11. Pain experienced at Day 14 post-randomisation

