# **11. ECONOMIC EVALUATION**

A full within-trial cost-effectiveness analysis (CEA) will be conducted to estimate the incremental costeffectiveness of the dexamethasone intervention as compared to placebo.

Resources and costs of providing oral dexamethasone will be established. Participant health, social care and broader societal resource use will be captured at baseline, Day 14 and Day 90 using self-report resource use questionnaires. These are based on the ModRUM core module but tailored to the study population, as informed by the PAG and trial team. Nationally-recognised UK health and social care unit costs will be applied to the resource use data.

QALYs will be estimated using EQ-5D-5L data collected at baseline and to Day 90 follow-up. The 'cross-walk' algorithm will be used to provide QALY weights from the EQ-5D-3L UK general population valuation survey, in accordance with the current 'position statement' of the National Institute of Health and Care Excellence (NICE). Descriptive statistics will summarise costs and QALYs by the dexamethasone and placebo groups. Mixed effects linear regression models will be undertaken to test for differences in costs and QALYs. In line with the SAP, these models will adjust for age, sex, baseline pain, severity of cellulitis, antimicrobial therapy for this episode of cellulitis prior to attending urgent and emergency care (yes/no) and diabetes status as fixed effects and recruitment site as a random effect to account for potential between-site heterogeneity. In addition, the cost regression model will adjust for baseline costs, and the QALY model for baseline EQ-5D-5L values. The CEA will synthesise cost and outcome data to present incremental cost-effectiveness ratios for: i) the trial primary outcome, in the form of cost of total pain prevented over 3 days post-randomisation, and for ii) the policy relevant economic endpoint, cost per quality-adjusted life-year (QALY) at Day 90 follow-up.

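### Reducing analgesia use is a comparative secondary objective, but section 10.2.2 fixes a descriptive analysis with no between-group estimate or confidence interval

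*Protocol*

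**What the plan says.** Section 3.2 frames the secondary objectives as comparisons with placebo. Objective (b) reads "Reduces subsequent antimicrobial prescribing, analgesia usage and healthcare utilisation". Section 3.3.1 makes analgesia the third secondary endpoint: "Analgesia usage (number and type of analgesia taken over first 3 days) post-randomisation".

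Section 10.2.2 divides the secondary outcomes into modelled and described. On the continuous side, "a mixed effects linear regression model will be fitted for the secondary outcomes of PGI-I and pain at 14 days", with a repeated measures model for the daily PGI-I. Mixed effects logistic models are planned, if events allow, for "additional antibiotic use post-randomisation to Day 14, (re)admission to hospital by Day 14, any unscheduled health care use until Day 14 and recurrence of cellulitis", the last of these over 90 days. These yield adjusted differences or odds ratios with 95% confidence intervals, and unadjusted versions as well. Analgesia is on the other side: "A descriptive analysis will report, by allocated group, on compliance, the amount and type of analgesia taken over the first 3 days".

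Two general statements also bear on this. Section 10.2 puts estimation ahead of hypothesis testing throughout. The estimands paragraph of section 10.2.2 applies the primary outcome's estimand, a treatment effect, to all secondary outcomes.

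**The concern.** A question about whether the drug reduces something calls for a difference between groups and a statement of its uncertainty. A table by group supplies the ingredients but neither of those. This is what the protocol specifies, not a detail it leaves open for the SAP to fill.

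Analgesia is also a poor candidate for description only, because it is tied to the primary outcome. Section 8 gives all participants analgesia under local policies, and section 8.9 allows NSAIDs. Section 10.2.1 uses a treatment-policy strategy, so the AUC records pain as experienced with whatever analgesia was taken. If placebo participants take more, the pain difference narrows and part of any benefit appears as analgesic sparing. If use is similar, the pain difference can be read more directly. Choosing between these readings, particularly after a small or null pain result, requires a pre-specified analgesia contrast with an interval.

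**Working it through.** **1. Components of objective (b) against their analyses**

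| Component (section 3.2) | Outcome | Analysis in section 10.2.2 | Between-group estimate and 95% CI? |
|---|---|---|---|
| Antimicrobial prescribing | Additional antibiotics to Day 14 | Mixed effects logistic | Yes |
| Antimicrobial prescribing | Route, type and length of course | Descriptive | No, but the component has the model above |
| Healthcare utilisation | (Re)admission by Day 14 | Mixed effects logistic | Yes |
| Healthcare utilisation | Any unscheduled care to Day 14 | Mixed effects logistic | Yes |
| Analgesia usage | Number and type over 3 days | Descriptive | **No** |

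Analgesia is the only component of objective (b) with no modelled outcome.

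**2. Are the data available?** Current analgesia and analgesia over the previous 3 days are recorded at baseline (section 7.5). Analgesia over the first 3 days after randomisation is recorded at the Day 14 call, with a paper aide-memoire as prompt (sections 7.4 and 7.9). An estimate adjusted for baseline use can be built from these.

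**3. Would the planned sample support a useful estimate?** The plan's own sample size comes first (section 10.1: difference 10, SD 30, two-sided 5%, 90% power):

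- n per group = 2 × (1.960 + 1.282)² × 30² / 10² = 189.1, so 190 by the normal approximation; the t-test version gives 190.1, so 191.
- Power at 191 per group is 90.1% (t-test).
- 191 / (1 − 0.15) = 224.7, so 225 per group and 450 in total.

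The stated figures reproduce. They concern the primary outcome and serve here only to supply n = 191. The assumption is that 191 per group also give analgesia data at Day 14.

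- Continuous summary: 95% CI half-width = 1.96 × √(2/191) = 0.20 SD, unadjusted.
- Binary summary (any use of a given class): half-width = 1.96 × √(2p(1 − p)/191), with p the common proportion. For p = 0.5 it is 1.96 × √(0.50/191) = 0.100. For p = 0.3 or 0.7 it is 1.96 × √(0.42/191) = 0.092.

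The documents give no analgesia rates, so placebo rates of 30%, 50% and 70% are assumed. Power at 191 per group, two-sided 5%:

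| Placebo rate | 10-point reduction | 15-point reduction |
|---|---|---|
| 30% | 0.62 | 0.94 |
| 50% | 0.50 | 0.85 |
| 70% | 0.54 | 0.86 |

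An interval of about ±9 to ±10 percentage points is informative. It would separate a substantial analgesic-sparing effect from none, though not a small one.

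**The case against.** The best defence is that description was a deliberate choice and loses little. Amount and type will be shown by randomised group, so an imbalance will be visible, and if counts are given a reader can work out a crude difference and interval. The data are recalled at Day 14 from an aide-memoire that is not collected, and they mix several drug types. Antibiotic route, type and length are also described only, so analgesia is not uniquely treated.

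Much of this stands. It limits the harm and explains the choice. It does not remove the mismatch: a crude difference worked out by a reader is neither pre-specified nor adjusted, and antibiotic use has a modelled summary alongside its descriptive detail.

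Three stronger readings are tempting but not supported.

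- **That quality of life is never compared between groups.** Section 10.2.2 names no model for "Health-related quality of life, measured by EQ-5D-5L at Day 3, Day 14 and Day 90 post-randomisation". But section 11 says "QALYs will be estimated using EQ-5D-5L data collected at baseline and to Day 90 follow-up" and compares QALYs between groups by mixed effects regression adjusted for baseline EQ-5D-5L. A model for each timepoint is detail the SAP may supply.
- **That the secondary objectives go unanswered.** The objective "Improves quality of life and other patient reported outcomes" is informed by the PGI-I, Day 14 pain and QALY models. Most of objective (b) is modelled.
- **That analgesia costs the primary analysis a known amount of power.** The documents give no figure for how far analgesia would narrow the pain difference. Under treatment policy, pain with analgesia as taken is arguably the quantity being targeted. Analysing analgesia differently would not alter that power.

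**Conclusion.** The mismatch is real and confined to analgesia. One component of a stated comparative objective, and one listed secondary endpoint, has no planned effect estimate or confidence interval, although the sibling components do and the protocol says it favours estimation. The primary test, its sample size and its power are unaffected. What suffers is the answer to that component and the interpretation of the pain result.

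The conclusion about the missing estimate rests on the protocol's text alone. The statement that an estimate would be usefully precise rests on 191 per group with Day 14 analgesia data and on assumed usage of 30% to 70%. The direction and size of any analgesia difference are unknown.

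**What to change.** In section 10.2.2, keep the descriptive table and add an adjusted between-group estimate with 95% confidence interval for analgesia use over the first 3 days, built from the number and type already collected. One option is a mixed effects logistic model for use of a pre-specified analgesic class, with the covariates and random site effect used for the other secondary outcomes, plus baseline analgesia. The class and the derivation rule should be fixed before unblinding, and the result reported beside the primary outcome.

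The cost is a short amendment to the analysis text. No new data, visits or participants are needed. The downsides are one or two more secondary estimates without multiplicity adjustment, and reliance on Day 14 recall. Both should be stated when the estimate is reported.

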#### Estimands framework for secondary outcomes

For all secondary outcomes, the same estimands as with the primary outcome will apply (see section 10.2.1).

